#### **6.5.1.4. Derivation of Secondary Case Definition (CDC case definition) of COVID-19**

This is a secondary efficacy endpoint: the incidence of the first occurrence of COVID-19 cases meeting the secondary case definition, starting 14 days after the first dose of IP, and COVID-19 cases starting 14 days after the second dose of IP.

The secondary case definition of COVID-19 is defined by the following criteria:

- One systemic or respiratory symptoms: fever (temperature  $> 38^{\circ}\text{C}/\geq 100.4^{\circ}\text{F}$ ), or chills, cough, shortness of breath or difficulty breathing, fatigue, muscle aches, or body aches, headache, new loss of taste or smell, sore throat, congestion or runny nose, nausea, or vomiting or diarrhea, AND
- At least one positive RT-PCR test for SARS CoV-2

Date of the documented secondary definition of COVID-19 will be later date of:

- Date of the positive RT-PCR test (prompt by symptom)
- Date of eligible symptom for secondary definition of COVID-19, defined as the earliest date of first eligible symptom is reported

and the two dates should be within 14 days of each other.

Secondary case definition of COVID-19 cases will also be summarized based on tests performed after randomization, and based on tests performed at least 14 days after first dose of IP.

### **6.5.2. Analysis Method**

The number and percentage of subjects who had an event will be summarized in the PP Set for Efficacy.

The incidence rate will be provided by vaccination group, calculated as the number of cases divided by the total person-time. The 95% CI of the incidence rate will be calculated using the exact method (Poisson distribution) and adjusted by person-time.

VE is defined as 1 – ratio of incidence rate (mRNA-1273 vs. placebo). The 95% CI of the ratio will be calculated using the exact method conditional upon the total number of cases adjusted by the total person-time.

Person-time is defined as the total time from randomization date to the date of event, last date of study participation, censoring time, or efficacy data cutoff date, whichever is earlier.

Incidence rate and VE will also be analyzed by time period or by calendar month.

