### **5.6. Modified Intent-to-Treat-1 (mITT1) Set**

The mITT1 Set consists of all participants in the mITT Set excluding those who received the wrong treatment (i.e., at least one dose received in Part 1A is not as randomized).

Participants will be analyzed according to the treatment group to which they were randomized.

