### **5.7. Per-protocol (PP) Set for Efficacy**

The Per-protocol (PP) Set for Efficacy consists of all participants in the FAS who meet all the following criteria:

- a) Received planned doses of study vaccination
- b) Complied with the timing of second dose of injection
- c) Had a negative RT-PCR test for SARS-CoV-2 and a negative serology test based on bAb specific to SARS-CoV-2 nucleocapsid (as measured by *Roche Elecsys Anti-SARS-CoV-2 assay*) at baseline

d) Had no major protocol deviations that impact key or critical efficacy data.

Participants will be analyzed according to the treatment group to which they were randomized.

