## 6.5. Efficacy Analysis

Efficacy analyses will be performed using the FAS, mITT, mITT1 and PP Set for Efficacy. The mITT1 Set is the primary analysis set for efficacy analysis of cases starting from 14 days after first dose, and PP Set for Efficacy is the primary analysis set used in the efficacy analyses for cases starting 14 days after second dose, unless otherwise specified. Subjects will be included in the treatment group which they were randomized.

**Baseline SARS-CoV-2 status** is described in [Section 6.1](#). Baseline SARS-CoV-2 status, the serology test results based on *Roche Elecsys* assay at baseline, the RT-PCR test results at baseline will be summarized by treatment group.

Participants with baseline positive or missing SARS-CoV-2 status will be excluded from the PP Set for Efficacy.

In this study, the serology test results based on Roche Elecsys assay and the RT-PCR test results will be summarized by visit.

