### **6.5.3. Sensitivity Analysis**

Sensitivity analysis for these efficacy endpoints will be performed with the same methods described above based on the FAS, mITT Set, and mITT1 Set, and with cases counted starting at different time points.

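### Part 1A SAP: Section 6.5 makes mITT1 the primary set for cases from 14 days after dose 1, but 6.5.2 names only the per-protocol set and 6.5.3 treats mITT1 as sensitivity

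*SAP*

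**What the plan says.** All references are to the SAP for Part 1A.

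- **Section 6.5** assigns primary sets by counting start. For the early count, "The mITT1 Set is the primary analysis set for efficacy analysis of cases starting from 14 days after first dose". For the later count, "PP Set for Efficacy is the primary analysis set used in the efficacy analyses for cases starting 14 days after second dose, unless otherwise specified".
- **Section 6.5.2** says: "The number and percentage of subjects who had an event will be summarized in the PP Set for Efficacy". It does not distinguish counting starts. The sentences on incidence rate and VE that follow name no analysis set.
- **Section 6.5.3** plans sensitivity analyses by the same methods, "based on the FAS, mITT Set, and mITT1 Set, and with cases counted starting at different time points".
- **Section 5.7** defines the per-protocol (PP) Set for Efficacy. Criterion (a) is "Received planned doses of study vaccination" and criterion (b) is "Complied with the timing of second dose of injection".
- **Section 5.6** defines mITT1 with no dose-2 requirement: it "consists of all participants in the mITT Set excluding those who received the wrong treatment".
- **Sections 3.2 and 6.5.1.4** make the early count part of a listed secondary endpoint, CDC-definition COVID-19 "starting 14 days after the first dose of IP, and COVID-19 cases starting 14 days after the second dose of IP". Sections 6.5.1.1 and 6.5.1.2 add early counts of infection and asymptomatic infection as further summaries.

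**The concern.** Read alone, 6.5 settles the matter: mITT1 for the early count, PP for the later one. Read alone, 6.5.2 and 6.5.3 make PP the main set for every efficacy endpoint and mITT1 a sensitivity set. For the early count these cannot both hold, and two programmers could each defend a different lead table.

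The two sets differ in a way that matters for this endpoint. Counting starts at about Day 15, whereas PP membership depends on what happens around Day 29. Someone who becomes a case between those days may receive dose 2 late or not at all. That person stays in mITT1 but can drop out of PP, taking the case along. This is selection on something that follows, and may be caused by, the outcome. What is at stake is the lead VE estimate for a secondary endpoint, and whether its population is fixed before results are seen.

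**Working it through.** **1. The text by counting start**

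| Cases counted from | 6.5 | 6.5.2 | 6.5.3 | Consistent? |
|---|---|---|---|---|
| 14 days after dose 2 | PP primary | PP | mITT1 as sensitivity | Yes |
| 14 days after dose 1 | mITT1 primary | PP (no split made) | mITT1 as sensitivity | No |

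**2. Is there a figure to reproduce?** No. The SAP gives no attack rate, assumed VE, event target or expected share missing dose 2 for the efficacy endpoints. Everything below is illustration on assumed inputs.

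**3. Direction.** Suppose the same share d of early cases is excluded in both arms. Per unit of arm size,

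RR = [late vaccine + (1 - d) × early vaccine] / [late placebo + (1 - d) × early placebo], and VE = 1 - RR.

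Exclusion only takes weight from the early period, so RR moves towards its later value. VE rises if early protection is lower than later protection, stays put if they are equal, and falls if early protection is higher.

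**4. Size when early protection is lower.** Assume constant placebo risk, and relative risk 0.3 or 0.5 from Day 15 to Day 43 and 0.1 afterwards. Placebo units to Day 85 are 14 + 14 + 42 = 70. The cases at risk of exclusion are those in the first 14 units.

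*Relative risk 0.3:* vaccine units are 0.3 × 28 + 0.1 × 42 = 12.6.
- None excluded: 1 - 12.6/70 = 82.0%
- Half excluded: 1 - (12.6 - 2.1)/(70 - 7) = 1 - 10.5/63 = 83.3%
- All excluded: 1 - (12.6 - 4.2)/(70 - 14) = 1 - 8.4/56 = 85.0%

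*Relative risk 0.5:* vaccine units are 0.5 × 28 + 4.2 = 18.2.
- None excluded: 1 - 18.2/70 = 74.0%
- Half excluded: 1 - 14.7/63 = 76.7%
- All excluded: 1 - 11.2/56 = 80.0%

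To Day 209, placebo units are 14 + 14 + 166 = 194.
- Relative risk 0.3: 1 - 25.0/194 = 87.1%; half excluded, 1 - 22.9/187 = 87.8%; all excluded, 1 - 20.8/180 = 88.4%
- Relative risk 0.5: 1 - 30.6/194 = 84.2%; half excluded, 1 - 27.1/187 = 85.5%; all excluded, 1 - 23.6/180 = 86.9%

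The shift at Day 209 is thus 0.6 to 2.7 points.

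**5. The sign can reverse.** Take 2,000 and 1,000 participants, an assumed placebo attack rate of 2% per 30 days, and follow-up to Day 57. Expected placebo cases are 1,000 × 0.02/30 × 14 = 9.33 early (Day 15 to 28) and 1,000 × 0.02/30 × 29 = 19.33 later. The vaccine arm is twice as large, so VE = 1 - (vaccine cases / placebo cases)/2.

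- *Early VE 50%, later 90%* (vaccine cases 9.33 and 3.87): 1 - (13.20/28.67)/2 = 77.0%. Half excluded in both arms: 1 - (8.53/24.00)/2 = 82.2%. All excluded: 90.0%.
- *Early VE 93%, later 80%* (vaccine cases 1.31 and 7.73): 1 - (9.04/28.67)/2 = 84.2%. Half excluded in both arms: 1 - (8.39/24.00)/2 = 82.5%. All excluded: 80.0%.
- *Early VE 80%, later 90%, unequal exclusion* (50% of early vaccine cases, 80% of early placebo cases): 86.7% becomes 1 - (5.73/21.20)/2 = 86.5%.

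Bringing in person-time changes these values by no more than about 0.2 points.

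**The case against.** The strongest reply is that 6.5 is the only section that assigns primary roles, and it does so by counting start. Section 6.5.2 never uses the word primary and never mentions dose 1, so it can be taken as describing the post-dose-2 default. The clause on other specification in 6.5 follows the PP half of the sentence and need not open the mITT1 half to override. This is a fair reading, and the fix adopts it. It does not remove the conflict: 6.5.3 classes mITT1 as sensitivity for these endpoints without exception, and nothing in 6.5.2 limits it to later counts.

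A reader might infer that the plan removes early cases and so inflates VE. The documents do not support that:

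- Section 6.5.2 ties the PP set only to counts and percentages. That VE is also computed in PP is an inference, though a natural one, since PP is the only set named there and 6.5.3 carries the same methods over to the other sets.
- The mITT1 result is produced on any reading. Only its standing is unclear.
- Section 6.4.4 and Appendix E (footnote 3) allow the dose-2 visit to move to Day 29 + 21 days for pandemic disruption, including self-quarantine. Section 6.4.4 raises a stricter window only for the PP Immunogenicity Subset. Some early cases may therefore stay in the PP Set for Efficacy, and excluding all of them is an extreme.
- The SAP gives no one-dose protection or dose-2 failure rates, so the direction of any bias is conditional, as steps 3 and 5 of the check show.

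**Conclusion.** The contradiction stands, and it is confined to cases counted from 14 days after dose 1, chiefly the CDC-definition secondary endpoint. If the PP set were used there, some early cases could be excluded because of what followed the event, and VE may be biased: upward if protection before dose 2 is lower than after it, otherwise not. On the assumed inputs with lower early protection in step 4, the shift is 1.3 to 6.0 points at Day 85 and 0.6 to 2.7 points at Day 209, for half to all of the Day 15-29 cases excluded. These figures rest wholly on assumed risks and exclusion shares.

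The consequence is limited. For counts from 14 days after dose 2 the three sections agree. The hypothesis tests in Section 4.2 concern immunogenicity only, so no success criterion is touched. It is still worth correcting, because the lead population for a secondary efficacy endpoint should not be open to choice.

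**What to change.** In 6.5.2, state that event counts and percentages, incidence rates and VE use mITT1 as the primary set for cases counted from 14 days after dose 1, and the PP Set for Efficacy for cases counted from 14 days after dose 2. Naming the set for rates and VE as well as counts closes the gap in that section. In 6.5.3, limit the sensitivity sets to those that are not primary for the counting start in question, so that mITT1 is a sensitivity set for post-dose-2 counts only.

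The change should stop there. Section 6.5.1.4 also mentions cases from randomization, but 6.5 sets no primary population for that count, so there is no stated rule to align with.

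The cost is a few sentences. Both sets are already defined and both analyses already planned.

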**Table 2. Derivation for SARS-CoV-2 Infection**

Baseline SARS-CoV-2 Status	Post-baseline assessments		Endpoint: SARS-CoV-2 infection
	PCR test post baseline	bAb levels against SARS-CoV-2 Nucleocapsid	
Negative at Baseline	Positive (either at scheduled NP swab test, or at symptom-prompt NP swab test)		Case
Negative at Baseline		Positive (at scheduled Day 57 visit or later) as measured by Roche Elecsys	Case

The date of documented infection will be the earlier of:

- Date of positive post-baseline RT-PCR result, or
- Date of positive serology test result based on bAb specific to SARS-CoV-2 nucleocapsid

The time to the first SARS-CoV-2 infection will be calculated as:

Time to the 1st SARS-CoV-2 infection = Date of the 1st documented infection – Date of randomization + 1.

Cases will be counted starting 14 days after the second injection, i.e. date of documented infection – Date of the 2nd injection  $\geq$  14.

SARS-CoV-2 infection cases will also be summarized based on tests performed at least 14 days after first dose of IP.

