**Table 1. Derivation for SARS-CoV-2 Infection**

Baseline SARS-CoV-2 Status	Post-baseline assessments		Endpoint: SARS-CoV-2 infection
	PCR test post baseline	bAb levels against SARS-CoV-2 Nucleocapsid	
Negative at Baseline of each part	Positive (either at scheduled NP swab test, or at exposure or symptom-prompt NP swab test)		Case

Negative at Baseline of each part	Positive (at scheduled post-baseline visits) as measured by Roche Elecsys	Case
--------------------------------------	---	------

The date of documented infection will be the earlier of:

- Date of positive post-baseline RT-PCR result, or
- Date of positive serology test result based on bAb specific to SARS-CoV-2 nucleocapsid

In long-term analysis (including Part 1B), SARS-CoV-2 infection cases will be counted starting 14 days after the second injection of mRNA-1273, i.e. date of documented infection - Date of the 2nd injection  $\geq$  14. SARS-CoV-2 infection cases will also be summarized based on tests performed at least 14 days after first dose of IP.

In Part 1C-1, SARS-CoV-2 infection cases will be counted starting 14 days after the booster dose of mRNA-1273, i.e. date of documented infection - Date of the booster injection  $\geq$  14.

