#### 6.5.1.3.Derivation of COVID-19

This is a exploratory efficacy endpoint: the incidence of the first occurrence of COVID-19 starting 14 days after the second dose of IP in long-term (including Part 1B), Part 2 and Part 3, cases counted starting 14 days after the first dose of IP in Part 3, and cases counted starting 14 days after the booster dose of mRNA-1273 in Part 1C-1 and Part 1C-2.

COVID-19 is defined as symptomatic disease based on the criteria specified in [Section 3.2](#). Cases are defined as participants meeting clinical criteria based on both symptoms for COVID-19 and positive RT-PCR test results.

Surveillance for COVID-19 symptoms will be conducted via biweekly telephone calls or eDiary. Subjects reporting COVID-19 symptoms, as defined in [Section 7.3.2 of the protocol](#), will be arranged an illness visit to collect an NP swab.

For this efficacy endpoint, a COVID-19 case will be identified as a positive post-baseline RT-PCR test result, together with eligible symptoms, i.e. a positive PCR result of the eligible symptoms summarized below in Table 2.

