### **6.5.2. Analysis Method**

The number and percentage of subjects who had an event will be summarized in the mITT1 Set for the long-term analysis and Part 1C-1 booster dose phase analysis, and FAS for Part 1C-2, Part 2 and Part 3 analysis.

The incidence rate will be provided by vaccination group if applicable, calculated as the number of cases divided by the total person-time. The 95% CI of the incidence rate will be calculated using the exact method (Poisson distribution) and adjusted by person-time.

Person-time is defined as the total time from date of the 1st dose of each part to the date of event, dose date in next part, last date of study participation, censoring time, or efficacy data cutoff date, whichever is earlier.

Incidence rate will also be analyzed by time period or by calendar month as applicable.

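### Person-time starts at randomization or the first dose of the part, but the main efficacy endpoints count cases only from 14 days after dose 2 or the booster, so those absolute incidence rates are understated by an amount that depends on follow-up

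*SAP*

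**What the plan says.** **Denominator.** Part 1A SAP, Section 6.5.2: "Person-time is defined as the total time from randomization date to the date of event, last date of study participation, censoring time", or the efficacy data cutoff, if earlier. No other start is given for any endpoint. Section 6.5.2 of the second SAP, which covers Parts 1B, 1C, 2 and 3, defines it as the "total time from date of the 1st dose of each part to the date of event, dose date in next part", with the usual later stops.

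**Numerator.** Part 1A SAP, Sections 6.5.1.1 and 6.5.1.3: "Cases will be counted starting 14 days after the second injection". Second SAP, Section 6.5.1.1, for the homologous booster: "SARS-CoV-2 infection cases will be counted starting 14 days after the booster dose of mRNA-1273". Second SAP, Section 6.5.1.3, for COVID-19: "starting 14 days after the second dose of IP in long-term (including Part 1B), Part 2 and Part 3", with Part 3 also counted from 14 days after Dose 1. Section 6.5.1.4 follows the same pattern for the CDC definition.

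**Other counting starts.** In Part 1A, CDC-definition cases are also summarized "based on tests performed after randomization, and based on tests performed at least 14 days after first dose of IP". Infection and asymptomatic infection also have a count from 14 days after dose 1 (Sections 6.5.1.1 and 6.5.1.2).

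Neither SAP removes from the denominator the time before counting opens. Both also plan rates by time period or calendar month and give no separate person-time rule for them.

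**The concern.** An incidence rate needs a numerator and denominator that cover the same time at risk. Here one denominator serves three case-counting starts and matches only the count from randomization. For the other counts, each participant adds a fixed block of time in which a case cannot be recorded. The shorter the follow-up, the larger that block's share and the lower the reported rate.

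The analysis sets make the mismatch wider. Section 6.5.3 of the Part 1A SAP applies the same method to the FAS, mITT and mITT1 sets, and the second SAP uses mITT1 for the long-term analysis. These sets can contain participants who never received dose 2. Such participants cannot become a case counted after dose 2, yet the rule credits them with person-time.

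At stake are the size of the reported rates and any reading of them across cohorts, data cuts or study parts. VE is at stake only if follow-up differs between the randomized arms.

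**Working it through.** The SAPs state no incidence rate, VE, event count or efficacy power, so there is no plan figure to reproduce. The size has to be worked out from the schedule.

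**Inputs**
- Randomization at the Day 1 visit (Part 1A SAP, Section 4.4); doses on Day 1 and Day 29 (Section 4.1.1.1).
- Time before counting opens, L: 28 + 14 = 42 days for dose-2 counts. With dose 2 at Day 29 + 21 (Section 6.4.4 and Appendix E), 28 + 21 + 14 = 63 days. For booster or dose-1 counts, 14 days.
- Part 1B crossover: dose 2 has a window of -3/+7 days (Appendix F), so L can be as short as 28 - 3 + 14 = 39 days; 42 is used below.
- Part 3, two doses: Dose 2 at Day 181 and about one month of further follow-up (Section 4.1.3), so L = 180 + 14 = 194 days.
- Follow-up F, in days from the person-time start: assumed from scheduled visits, because actual follow-up is not given.

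**Formula.** With a constant hazard and rare events, reported rate / rate in the counting window = (F - L)/F, so the understatement is L/F.

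| Count | Follow-up to | L/F | Understated by |
|---|---|---|---|
| Part 1A, dose 2 + 14 | Day 57 | 42/56 | 75.0% |
| same | Day 209 | 42/208 | 20.2% |
| same, dose 2 at Day 29 + 21 | Day 209 | 63/208 | 30.3% |
| same | Day 394 | 42/393 | 10.7% |
| Part 1B crossover, dose 2 + 14 | OL-D113 | 42/112 | 37.5% |
| same | OL-D178 | 42/177 | 23.7% |
| Booster + 14 | BD-D29 | 14/28 | 50.0% |
| same | BD-D181 | 14/180 | 7.8% |
| same | BD-D361 | 14/360 | 3.9% |
| Part 1A, dose 1 + 14 | Day 209 | 14/208 | 6.7% |
| Part 3, Dose 1 + 14 | Day 181 | 14/180 | 7.8% |
| Part 3, Dose 2 + 14 | Day 209 | 194/208 | 93.3% |
| Part 1A, from randomization | any | 0/F | 0% |

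**Effect on VE.** Expected values used exponential event times, with person-time stopped at the event. Per person, cases = 1 - exp(-λ(F - L)), time at risk = cases/λ, and person-time under the plan = cases/λ + L.

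*Equal follow-up.* With an assumed placebo hazard of 50 per 1,000 person-years, true VE of 80% and 208 days in both arms, the plan gives 8.0 and 39.8 per 1,000. Aligned person-time gives 10.0 and 50.0. VE is 80.0% either way. Over true VE of 50%, 80% and 93% and placebo hazards of 50 and 200 per 1,000 person-years, VE moves by at most about 0.3 percentage points. An exact-interval example with 4 vs 20 cases, 2:1 allocation and equal follow-up gives 90.0% (70.1 to 97.5) under both rules.

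*Unequal follow-up (assumed), true VE 80%, same hazard.*

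| Vaccine days | Placebo days | VE under the plan | VE aligned |
|---|---|---|---|
| 208 | 152 | 77.9% | 80.0% |
| 208 | 120 | 75.4% | 80.0% |
| 208 | 90 | 70.0% | 80.0% |
| 152 | 208 | 81.8% | 80.0% |

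Hand check of the 208 vs 120 row with the rare-event formula: 1 - 0.20 × (166/208)/(78/120) = 1 - 0.20 × 0.798/0.650 = 0.754.

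**The case against.** The strongest defence is that this is a consistent and disclosed convention. The Part 1A SAP uses randomization as the start of the efficacy period, as the time-to-event origin and as the person-time origin. The result can be read as a rate per person-time since randomization. Both randomized arms carry the same lag, so it cancels in VE. The long-term cohorts are summarized descriptively, without group comparison (Part 1A SAP, Section 6.6). Efficacy is secondary in Part 1A and exploratory elsewhere, and it has no success criterion.

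Most of that stands and limits the harm. It does not rescue the absolute rates. One origin cannot suit three counting starts, and disclosing a diluted rate does not make it comparable with one diluted by a different share.

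Four stronger readings are tempting, and the documents do not support them:

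- *Every rate is understated.* CDC-definition cases counted from randomization are matched, and counts from 14 days after dose 1 lose only about 7% to 8% at the follow-up shown.
- *VE is biased.* This needs follow-up to differ by arm. Blinded efficacy follow-up ends person by person, at unblinding, non-study vaccination or first Part 1B injection among other events (Part 1A SAP, Section 6.1), so a difference is possible. No difference is stated, and all ongoing participants are offered the decision visit.
- *Participants infected before counting opens keep adding person-time.* The rule also stops at the event or at a censoring time, and neither SAP says how an early infection is treated. That is a gap, not a stated rule.
- *Calendar-month rates are distorted most in the early months.* Without a stated person-time rule for those analyses, this cannot be judged.

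**Conclusion.** The mismatch is real and is written into both Sections 6.5.2. Followed exactly, the plan understates absolute rates counted from 14 days after dose 2 by about 20% at Day 209, 11% at Day 394 and 24% for crossover participants at OL-D178. Booster rates are understated by 4% to 8% between BD-D361 and BD-D181. The extreme case is the Part 3 count from 14 days after Dose 2, with 14 countable days out of 208. Sections 6.5.1.3 and 6.5.1.4 of the second SAP keep that count, although Section 3.5.4 lists only the count after Dose 1. Because the shortfall depends on follow-up, these rates should not be compared across cohorts, data cuts or parts.

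The sizes rest on scheduled follow-up, on-time dosing and a constant hazard; the actual values are not in the documents. They fit the symptomatic COVID-19 endpoints best. For the infection endpoint, a seroconversion found at Day 57 may reflect an infection acquired before counting opened, so the percentage is less exact there. Long-term efficacy follow-up in the main analysis ends at the booster (second SAP, Section 6.1), so the Day 394 figure applies only to participants not boosted by then.

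This should be fixed, but it does not threaten the primary immunogenicity conclusions, which do not use these rates.

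**What to change.** In Section 6.5.2 of both SAPs, define person-time separately for each endpoint and counting start:

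- Begin on the date case counting opens: 14 days after dose 2, dose 1 or the booster, as applicable.
- Include only participants who received the required dose, are still under follow-up on that date and have not already had that endpoint's event.
- Keep the randomization or first-dose origin only for cases counted from that date.
- State the person-time rule for the time-period and calendar-month analyses.
- State how an infection documented before counting opens is handled. Any wider exclusion of such participants changes the population being described, so make it a sensitivity analysis, separate from the denominator correction.

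The cost is SAP wording and one derived start date per counting rule, with no new data. Reported rates will rise. Where rates have already been reported under the present rule, show both denominators side by side and record the change.
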